Study Design	
This is a bilateral, non-dispensing, randomized, partially-masked (subject), four visits, single site, 3-period by 3-treatment crossover study. There are 3 levels of randomization in this study. (1) Driving time (Day and Night) (2) Study Lens (Test, Control 1 and Control 2) and (3) driving route (Route 1, Route 2 and Route 3). Hazard and pedestrian locations will be randomized between each route.
 
There will be a total of 4 visits:
 
 1. Visit 1: Screening, preliminary contact lens fit 2. Visit 2: Laboratory based measures of binocular visual performance (test and control items) 3. Visit 3: Closed circuit on road driving assessment (day or night time based on randomization) 4. Visit 4: Closed circuit on road driving assessment (day or night time based on randomization) 
See the flow chart at the end of the synopsis table for the schematic of the study visits and procedures of main observations.

Sample Size	Twenty-eight (28) eligible subjects will be enrolled and 24 are targeted to complete the study
Study Duration	
Three months are allotted from first subject first visit (FSFV) to last subject last visit (LSLV).
 
Per subject:
 
 • Visits 1-4 completed within 8 weeks accounting for weather and access to the driving track • Visits 1, 2 and 3 will be separated by at least 24 hours • Visits 3 and 4 will be separated by at least one week
Anticipated Study Population	Habitual soft contact lens wearers aged between 20-49 years (of any ethnicity)

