2.2.2. Secondary Endpoint(s)

Binocular visual performance:

The following measurements will be used to assess the performance of the test and control products in a controlled laboratory setting which simulate a wide range of visual conditions encountered while driving.

1. High luminance (~500 lux) high contrast (90%) LogMAR distance visual acuity
2. High luminance (~500 lux) low contrast (10%) LogMAR distance visual acuity
3. Low luminance (~1 lux) high contrast (90%) LogMAR distance visual acuity
4. High luminance (~500 lux) contrast threshold (Pelli-Robson chart)
5. Low luminance (~1 lux) contrast threshold (Mesotest II instrument by Oculus, Germany)

The order of the vision tests will be randomized for each condition. The ETDRS logMAR chart will be used, which is scored on a letter by letter basis (-0.02 log units per letter correctly identified). A number of different EDTRS charts will be used to reduce potential learning effects. Letter contrast sensitivity will also be determined binocularly using the Pelli-Robson chart, scored on a letter by letter basis (0.05 log units per each letter correctly identified). The ETDRS logMAR chart and the Pelli-Robson contrast sensitivity chart are validated techniques routinely used in research to accurately quantify visual performance. Room illuminance will be controlled using dimmer switches and quantified using a lux meter.

There will be two secondary endpoints considered from binocular visual performance evaluation:

- Low luminance (~1 lux) high contrast (90%) distance visual acuity
- Low luminance (~1 lux) contrast threshold

During low luminance contrast threshold evaluation, five Landolt C targets in random orientation will be presented for each of four contrast levels 95%, 80%, 63% and 50%. Participants will be asked to correctly identify the orientation of the Landolt C. The number of correct response will be recorded for each contrast level. This entire test will be done with and without the presence of a glare source.

Sign recognition (percentage)

Participants will be instructed to report the identity of a percentage of the standard road signs (typically about 42 signs dependent on the route travelled) containing about 65 items of information as they drive around the circuit. We will also measure the recognition distance using the in-vehicle measurement system for one specific road sign while the participant is driving.

Hazard avoidance:

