Participants will be required to report and avoid hitting any of nine large, low contrast grey foam “hazards” (220 cm x 80 cm x 15 cm) positioned orthogonally in the driving lane along the roadway, the locations of which will be randomized between trials.

Pedestrian recognition distance:

The in-vehicle measurement system will be utilized to determine the distance at which the participant (as a driver) first recognizes the presence of two pedestrians positioned at the side of the road. An experimenter will act as the pedestrian and “walk in-place” at the end of a 400 m straight section of roadway which starts and finishes at approximately the same elevation, but features a dip halfway along its length. The pedestrian will not be surrounded by any visual clutter or lighting. To reduce expectancy effects, a series of four flashing LEDs and four retro-reflective bollards will be positioned around the circuit to increase the instances of flashing

lights and retro-reflective material being presented to the driver. Figure 2 shows an example of a low contrast hazard (grey foam) in the driving lane in front of some retroreflective bollards and signage.

Figure 2
Example of low contrast hazards (grey foam) in driving lane

On each lap the pedestrian will walk in place as the test vehicle approaches, facing directly towards the oncoming vehicle; this allows for the inclusion of naturalistic motion and ensures the safety of the pedestrian. The pedestrian will wear biomotion reflective strips on the moveable joints, which has been shown to be a configuration that allows good discrimination between different levels of spherical blur².

The main dependent variable is the driver's response distance to the pedestrian which is defined as the distance from the test vehicle to the pedestrian at that moment when the response button is pressed to indicate recognition of the presence of the pedestrian at the side of the road.

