4.2. Study Design Rationale

Crossover designs are a well-established study design in which subjects are exposed to multiple treatments during different time periods. This design was considered to reduce the influence of potential confounding factors such as age, gender, vision correction and driving performance. A washout period of 20 minutes or more between driving assessments is built in from the 15-minute lens settling time and the 5-minute acclimation inside the car. This will help reduce any potential carry-over effect. Since subjects will be performing the same task repeatedly driving track conditions are randomized for each test article in order to further reduce any potential bias.

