5. TEST ARTICLE ALLOCATION AND MASKING

5.1. Test Article Allocation

Participants will wear all study lenses in a bilateral fashion. There will be three levels of randomization in this study: (1) Sequence of driving time (Day and Night) (2) Sequence of lens wear (Test, Control1 and Control2) and (3) Driving Route (A, B, C). Hazard and pedestrian locations will be randomized for each driving route.

Subjects will be first randomly assigned to one of two possible driving time sequences (Day/Night and Night/Day) using a 2x2 crossover design. Within each driving time (Day and Night) subjects will be randomly assigned to one of six possible lens wear sequences using a 3x3 Williams crossover design:

Table 1: 3x3 Williams design

Sequence	Period1	Period 2	Period 3
1	Test	Control 1	Control 2
2	Test	Control 2	Control 1
3	Control 1	Test	Control 2
4	Control 1	Control 2	Test
5	Control 2	Test	Control 1
6	Control 2	Control 1	Test

This design is balanced with respect to first carry-over effect as every treatment follows every other treatment the same number of times.

Within each time and lens type combination subjects will be randomized to a driving route (Route1, Route2 and Route3) to further reduce the potential for treatment bias. The randomization scheme will be generated using the PROC PLAN procedure from SAS Software Version 9.4 or higher (SAS Institute, Cary, NC). The study site must follow the randomization scheme provided and complete enrollment according to the randomization list and not pre-select or assign subjects.

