3.6.	Randomization	
Refer to pre-determined randomization order of testing (counter balancing) for the three test treatments. The final contact lens powers found in Visit 1 will be used.
 
 • Test contact lenses (worn with spectacle frame without lenses) • OASYS clear contact lenses (worn with spectacle frame without lenses) • OASYS clear contact lenses (worn with photochromic spectacles) 	
3.7.	Lens Insertion	
The Investigator or the subject inserts the study lenses. Record the time of lens insertion. Check for lens damage under the slit lamp before proceeding with lens settling. Replace damaged lenses if applicable.
	
3.8.	Lens Settling	
Allow the study lenses to settle for a minimum of 15 minutes.
 
Note: for nighttime testing, sufficient time is allowed for the subject to dark adapt.
	
3.9.	Pupillometry	
Measure the right eye pupil diameter during distance fixation (3 measures) using NeurOptics Pupillometer while subject seated in vehicle.
 
EDC: record pupil diameters in mm (0.1 mm increments)
	
3.10.	Illuminance levels	
Measurement of lighting level on the track outside the vehicle and at the plane of the eye in the vehicle.
 
 • For daytime testing, the illuminance must be > 1000 lux. • For nighttime testing, the illuminance must be < 10 lux. 
EDC: record outside and inside illuminance in lux rounded to the nearest whole number.
	

Visit 3: Closed-circuit on-road driving performance 1 (Day/night condition based on randomization)			
Step	Procedure	Details	
3.11.	Driving assessment	
Subject performs three laps of the circuit while under assessment. Measurements recorded include:
 
 1. Sign recognition 
 a. EDC: record % signs correctly identified b. EDC: record distance to signs in meters 2. Hazard avoidance 
 a. EDC: record % hazards hit 3. Driving time 
 a. EDC: record lap time in seconds b. EDC: record the % time in wrong lane 4. Pedestrian recognition distance 
 a. EDC: record distance to recognition in meters 
A composite driving Z score will be calculated afterwards using measures listed above.
	
3.12.	Subjective Questionnaire	Administer subjective questionnaire regarding driving task just completed. This will be a paper-administered questionnaire.	Appendix A

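### Route is randomised within each time-by-lens combination with no rule that a subject's three routes in a session differ or balance over lenses, and route is not in the driving models

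*Protocol*

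**What the plan says.** Protocol 5.1 (repeated in SAP 1.6) sets three levels of randomisation. Lens order has an explicit six-sequence Williams table and a statement of its balance. Route has one sentence: "Within each time and lens type combination subjects will be randomized to a driving route". PROC PLAN is named as the generator, but the constraints placed on routes are not given.

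On the layout of targets, the wording varies:

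- Protocol synopsis, Study Design: "Hazard and pedestrian locations will be randomized between each route".
- Protocol 5.1 (same in SAP 1.6): "Hazard and pedestrian locations will be randomized for each driving route".
- Protocol 2.2.2, on the hazards (same in SAP 6.1): "the locations of which will be randomized between trials".
- Protocol 4.2: "driving track conditions are randomized for each test article in order to further reduce any potential bias".

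The road signs are described as "typically about 42 signs dependent on the route travelled" (Protocol 2.2.2, SAP 6.1), and no text says they are changed between drives. At step 3.11 of Visit 3, "Subject performs three laps of the circuit while under assessment", and step 3.14 repeats this for the other two lens conditions. The primary model in SAP 5.2 and its code in Appendix A contain sequence, period, lens, carry-over, driving time and interactions. Route is not a term there, nor in the models for signs, hazards and recognition distances.

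**The concern.** Three lenses and three routes per session invite a one-to-one assignment, but the written rule does not ask for one. A subject who meets a route a second time in a session has already driven three assessed laps on it. Four of the six composite measures depend on finding or reading targets: sign distance, sign percentage, hazards and pedestrian distance. The two sign measures have no redraw rule at all, so a repeated route repeats its signs.

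Two things are at stake. Repeats and chance imbalance of routes over lenses add noise to Test minus Control 1, and no model term absorbs it. And if remembered positions stand in for vision, a real lens deficit could show less on repeated routes. In a non-inferiority comparison with a margin of -0.25, dilution toward zero is the unsafe direction. The period and carry-over terms do not isolate this, because repetition would occur in some subjects and not in others within the same period.

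**Working it through.** The plan gives no figure on this point, so there is none to reproduce. **Inputs from the documents:** three lenses and three routes per session, 24 completers, margin -0.25. **Assumptions:** independent, equally likely route draws; a residual (within-subject) variance of 0.05, which is what the power table's between-subject variance of 0.05 implies at ICC 0.50, since 0.05 × (1 - 0.50)/0.50 = 0.05.

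**1. How often a route repeats, if draws are independent.** There are 3³ = 27 equally likely route triples.
- All three different: 3! = 6, so 6/27 = 22.2%.
- At least one repeat: 21/27 = 77.8%, or 24 × 0.778 = 18.7 of 24 sessions.
- Test and Control 1 on the same route: 9/27 = 1/3, or 8 of 24 expected.
- Drives on a route already seen that session: 0 in period 1, 1/3 in period 2, and (1/3)(1/3) + (2/3)(2/3) = 5/9 in period 3. The average is (0 + 1/3 + 5/9)/3 = 8/27 = 29.6%.

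**2. If memory adds a fixed gain on a repeated route.** The documents give no size, so gains of 0.1, 0.25 and 0.5 Z units were assumed and simulated (24 subjects, Williams sequences). The mean error in Test minus Control 1 stayed within 0.003 of zero. The SD of the estimate was:

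| Assumed gain | SD |
|---|---|
| 0 | 0.064 |
| 0.1 | 0.066 |
| 0.25 | 0.072 |
| 0.5 | 0.090 |

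This is noise, with no shift toward either lens.

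**3. If memory masks a true deficit on repeated routes.** Let m be the share masked. The expected difference is -0.25 × (1 - m × 8/27).
- m = 0: -0.25.
- m = 0.5: -0.25 × (1 - 4/27) = -0.213.
- m = 1: -0.25 × (1 - 8/27) = -0.176.

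**4. What route differences do to precision.** Assume route effects of -0.2, 0 and +0.2 (SD 0.2 with divisor 2). Their variance over one random draw is 0.08/3 = 0.0267, and the covariance of two draws without replacement is -0.0267/2 = -0.0133. With no route term, the SD of the mean Test minus Control 1 is:
- Independent draws: √[(2 × 0.0267 + 2 × 0.05)/24] = 0.080.
- Unconstrained permutation: √[(2 × (0.0267 + 0.0133) + 2 × 0.05)/24] = 0.087.
- Balanced, 8 per lens-route cell: route effects cancel, √[(2 × 0.05)/24] = 0.065.

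Simulation agrees (0.079, 0.086 and 0.065).

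Balance alone is not enough. Without a route term the route differences stay in the residual. Their sum of squares is 24 × (0.04 + 0 + 0.04) = 1.92. With subject, lens and period fitted there are 72 - 24 - 2 - 2 = 44 residual degrees of freedom, so the residual mean square is about 0.05 + 1.92/44 = 0.094. The reported SE is then √(2 × 0.094/24) = 0.088, against a true SD of 0.065. A mixed-model simulation gave 0.085. The interval would be too wide unless route is fitted.

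**5. Is balance feasible?** 24 subjects × 3 drives = 72, and 72/9 lens-route cells = 8. A search found a list of 24 with four subjects per Williams sequence, 8 per lens-route cell and 8 per route-period cell. Fully crossing a three-row Latin square of routes with the six sequences needs multiples of 18, which 24 is not.

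**The case against.** A reader might infer three stronger things, and the documents do not support them.

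*Routes are drawn independently for each lens.* The text does not say so. A PROC PLAN list that uses each route once per session is compatible with it, as is one with equal numbers per route within each lens. The percentages in step 1 therefore depend on one reading. What stands is that the constraint is not stated, whereas the same section spells out the balance of lens order.

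*The hazard layout repeats with the route.* Protocol 2.2.2 and SAP 6.1 redraw hazards between trials, and step 3.13 uses the word trial for a single lens condition. Protocol 4.2 adds that track conditions are randomised for each test article. On that wording, hazards are not learned along with the route. The per-route sentences conflict with it and need reconciling, but they do not show a design flaw. The signs have no redraw rule, and neither 2.2.2 nor SAP 6.1 gives pedestrian positions an explicit between-trials rule.

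*Course memory biases the comparison toward non-inferiority.* Repeats are random with respect to lens, lens order is balanced, and period and carry-over are modelled. An additive gain leaves the expected difference unchanged and widens the interval, which makes non-inferiority harder to show. Dilution requires the further assumption that memory hides a true deficit.

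Two objections to the remedy also stand. Permuting routes without balance or a route term can lower precision (step 4). And no scheme removes course memory: six drives on three routes mean that each route is still driven twice across the day and night visits.

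**Conclusion.** The point holds as an unstated constraint with a cheap improvement. The written rule permits a route and its signs to recur under the next lens, and leaves lens-by-route balance unspecified. Under independent draws this would affect about 78% of sessions, and the primary contrast directly in about one third. The expected consequence is added variance. Its size depends on memory gains and route differences that the documents do not give; under the assumed values the SD rises from about 0.065 to between 0.066 and 0.090. Anti-conservative dilution is conditional on masking: a true -0.25 would appear as anything from -0.25 (none) to about -0.18 (complete masking on every repeat). This should be corrected, but it is not evidence that the primary comparison is biased.

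**What to change.** 1. In Protocol 5.1 and SAP 1.6, state that the three routes are assigned without replacement within each visit, and that each lens meets each route equally often (8 per lens-route cell at 24 subjects). Describe the balance as marginal, and as approximate after dropout.
2. Add route as a fixed effect in the driving models of SAP 5.2, SAP 6.2 and Appendix A. The constraint deals with within-session repeats, and the route term gives an SE that matches the design. The two should be adopted together.
3. Use one layout rule for hazards and one for pedestrians throughout, reconciling the synopsis, Protocol 5.1 and SAP 1.6 with Protocol 2.2.2, Protocol 4.2 and SAP 6.1.

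If the existing list already uses each route once per session and balances routes over lenses, a sentence saying so settles item 1. If it does not, the list should be regenerated before the first subject is randomised. If that is no longer possible, fit the route term and report how many subjects drove Test and Control 1 on the same route.

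The cost is a more constrained list, two model degrees of freedom and a few edited sentences. No extra subjects or visits are needed.

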5.2. Masking

Every effort will be made to mask both the subject and the investigator, in order reduce potential bias where possible. Subjects will be masked to the identity of the investigational product when only a contact lens correction is worn. However, if subjects perceive a change in light levels during Test contact lens wear, they may become aware of the product being tested.

Subjects will also be aware of the test condition when the ACUVUE® OASYS® Brand Contact Lenses with HYDRACLEAR® PLUS is worn with Transitions® XTRActive™ – Gray Spectacles (Control 2) as the other test conditions will involve contact lens wear with a spectacle frame without spectacle lenses.

Investigators involved in the on-road driving data collection (clinical personnel within the vehicle) will be partially-masked as to the identity of the investigational product (i.e. another investigator will fit the contact lenses prior to the driving assessment).

5.3. Procedures for Maintaining and Breaking Randomization Codes

Under normal circumstances, the mask should not be broken until all subjects have completed the study and the database is finalized. Otherwise, the mask should be broken only if specific emergency treatment/course of action would be dictated by knowing the treatment status of the subject. In such cases, the Investigator may, in an emergency, contact the medical monitor. In the event the mask is broken; the Sponsor must be informed as soon as possible. The date, time, and reason for the unmasking must be documented in the subject record. The Investigator is also advised not to reveal the study treatment assignment to the clinical site or Sponsor personnel.

6. STUDY INTERVENTION

6.1. Identity of Test Articles

The following contact lenses will be used in this study:

Table 2: Test Articles

	Test	Control 1	Control 2
Name	Senofilcon A-based contact lens with new UV-blocker (worn with spectacle frame without lenses)	ACUVUE® OASYS® Brand Contact Lenses with HYDRACLEAR® PLUS (worn with spectacle frame without lenses)	ACUVUE® OASYS® Brand Contact Lenses with HYDRACLEAR® PLUS worn Transitions® XTRActive™ – Gray Spectacles
Manufacturer	JJVC	JJVC	JJVC / TOI

	Test	Control 1	Control 2
Compass Protocol(s) and/or Lot Number or Other Identifier	██████████	Commercial ACUVUE OASYS	Commercial ACUVUE OASYS and plano Transitions spectacles
Lens Material	Senofilcon A	Senofilcon A	Senofilcon A XTRActive
Nominal Base Curve @ 22 °C	8.4	8.4	8.4
Nominal Diameter @ 22 °C	14.0	14.0	14.0
Nominal Distance Powers (D)	-1.00 through -6.00	-1.00 through -6.00	-1.00 through -6.00
Oxygen Permeability (Dk)	~ 103	~ 103	~ 103
Modality in Current Study	Daily wear	Daily wear	Daily wear
Replacement Frequency	Single use	Single use	Single use
Packaging Form (vial, blister, etc.)	Blister	Blister	Blister
Other distinguishing items	NA	NA	See spectacle table below

Approximately 30 Test lenses per sku will be needed for Visits 1, 2, 3 and 4. Since OASYS will be worn twice at each of these visits, approximately 60 control lenses per sku will be needed. Additional lenses may be shipped to cover any lenses lost, damaged, or heavy concentration on a particular power.

Examples of the spectacle frames are shown. The polycarbonate lenses will be 0.00 D in power and will contain the XTRActive photochromic agent from Transitions Optical Inc. The lenses will not contain an anti-reflective coating for a more valid comparison to the contact lenses. Half of the frames will have no lenses whatsoever and will be worn during the Test and OASYS trials to keep frame awareness the same as during the OASYS + photochromic spectacle trial.

Small unisex frames	Medium unisex frames	Large unisex frames

 • 2 with 0.00 D XTRActive lenses • 2 with no lenses 	
 • 2 with 0.00 D XTRActive lenses • 2 with no lenses 	
 • 2 with 0.00 D XTRActive lenses • 2 with no lenses
		

6.2. Ancillary Supplies/Products

This is a non-dispensing study. No contact lens care solutions are required. The use of Lens Plus OcuPure saline solution for rinsing the lenses and the use of preservative-free rewetting drops is permitted as needed.

6.3. Administration of Test Articles

Test articles will be worn by the subjects for the duration of the testing sessions. Subjects must meet all eligibility requirements set forth in this clinical protocol to be fit with the lenses.

